- Scientific Data Monitoring Committee
[name]. med. [name]
Full Professor of Obstetrics and Gynaecology, Robinson Research Institute, SAHMRI, University of Adelaide, Australia
[contact].

Scientific Advisory Board

- [name]. [name]
Full Professor of Obstetrics and Gynecology
Department of Women's and Children's Health, University of Liverpool, UK
[contact]

Sanitary device: The Arabin cervical pessary, which is CE-certified for preventing SPB (CE 0482 / EN ISO 13485: 2012 + AC:2012 annex III of the council directive 93/42 EEC).

Main objective: To assess the impact of a prophylactic treatment with a cervical pessary in women at high risk of spontaneous Preterm Birth (PTB) due to a history of previous preterm deliveries and/or a history of previous cervical surgery (conisation) on the children's survival without neurodevelopmental disability at the age of 3. Recruitment will be offered to all women at 12+0 -16+0 weeks of gestation with status after PTB in previous pregnancies and/or conisation.

Study design: Prospective Open-label Multicentre International Collaborative Randomized Controlled Trial, in parallel groups, based on intention to treat comparing the early placement of a cervical pessary with standard care management in cases of a singleton pregnancies at high-risk for PTB. The standard care arm (control group) shall receive a rescue cerclage in cases with cervical shortening. Therefore, serial cervical length measurements should be conducted onward the 12+0 week every 4 weeks.

Main outcome: Children's survival without neurodevelopmental disability at 3 years of age.

Study population: The study will be proposed to women with a singleton pregnancy at 12+0 – 16+0 weeks of gestation and a history of at least one previous preterm delivery and/or a history of previous cervical surgery attending the reference hospital and who do not fulfil the exclusion criteria. In this context, cases with previous preterm birth should only be considered, when birth occurred before the 34+0 week of pregnancy.

The patients will be informed of the intended therapeutic effect and possible side effects. If they agree and after obtaining their informed consent, they will be randomised according to either cervical pessary placement up to 37+0 weeks (= pessary group) or expectant management according to standard care and a

Confidential

McDonald cerclage placement as soon as a cervical shortening below 25 mm is diagnosed (=control arm).

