Hereby, patients of the control arm shall receive serial cervical length measurements by transvaginal ultrasound (TVS) every 4 weeks started at 12+0 weeks.

A cerclage may be indicated when the cervical length is below 25 mm.¹ (s. consort-diagram).

Sample size:

For sample size calculation, we assume a combined event rate for the primary outcome (long-term survival without neurodevelopmental disability at 3 years of follow up) of 8% for the pessary group and an event rate of 20% for the control group van't Hooft 2016. Group sample size of 121 in both groups achieve 80% power to detect this difference using a two-sided chi-square test with significance level alpha=5%. To account for a drop out rate around 25%, sample size of 155 in each group, overall n=310 women will be recruited.

Study calendar:

Starting recruitment: June, 1st, 2018

Finishing recruitment and follow-up: est. June 1st, 2023.

Final report: Sept. 1st, 2023.

Table of contents

1. General Information

- 1.1. Title, protocol identifying number and date.
- 1.2. Name and address of the Sponsor.
- 1.3. Name and title of the authorized person by the Sponsor to sign the protocol and the protocol amendments.
- 1.4. Name, title, addresses and telephone numbers of the medical experts of the Sponsor of the trial.
- 1.5. Name and title of all the researchers who are responsible for conducting the trial and address and telephone numbers of trial sites.
- 1.6. Name, title, address and telephone number of the qualified physician who is responsible for all medical decisions on each trial site.
- 1.7. Name and address of the medical departments or institutions that are involved in the trial.

2. Rationale

- 2.1. Justification of the relevance of the trial.
- 2.2. Description of the study population.
- 2.3. Name and description of the device under investigation.
- 2.4. Statement that testing will be performed according to the protocol, GCP and applicable legal requirements.

3. Objective

4. Design

- 4.1. Specific description of primary and secondary variables.
 - 4.1.1. Primary outcome.
 - 4.1.2. Secondary outcomes.
- 4.2. Description of the trial design.

Confidential

- 4.3. Flowchart.
- 4.4. Description of the medical device and treatment regimen.
- 4.5. Expected duration of subject's participation.
- 4.6. Completion and interruption criteria of the study or the subjects.
- 4.7. Maintenance of the randomization codes and test procedures of the trial.

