2.2. Description of the study population.

Women with a singleton pregnancy at 12 – 16 weeks of gestation and a history of at least one previous preterm delivery before 34+0 weeks and/or a history of previous cervical surgery attending the reference hospital and who do not fulfil the exclusion criteria the study will be proposed. The patients will be informed of the intended therapeutic effect and possible side effects. If they agree and after obtaining their informed consent, they will be randomised according to either usual management with rescue cerclage placement only when (and as soon as possible) a cervical shortening below 25 mm occurs (=control group) or cervical pessary placement (= pessary group).

Pessaries or cerclage shall be placed up to 37+0 weeks of gestation. In the control group serial cervical length measurements shall be conducted every 4 weeks in order to diagnose cervical shortening as soon as possible.

2.3. Name and description of the device under investigation.

The Arabin cervical pessary, which is CE-certified for preventing SPB (CE 0482 / EN ISO 13485: 2012 + AC:2012 annex III of the council directive 93/42 EEC).

See annex I.

2.4. Statement that testing will be performed according to protocol, GCP and applicable legal requirements.

The Clinical Trial will be conducted following the protocol, the GCP, and all legal requirements.

3. Objective

This study aims to investigate the benefit of a prophylactic cervical pessary treatment in women at high risk of PTB due to a history of at least one previous preterm delivery before 34+0 weeks and/or a history of previous cervical surgery on the children's long-term survival without neurodevelopmental disability.

Hereby, a standardized and validated test called 'Ages and Stages 3rd edition'²⁷ should evaluate the children's neurodevelopment. The test should be conducted by the parents and takes approximately 12 minutes. The questionnaires will be provided by the sponsor.

4. Design

4.1. Specific description of primary and secondary variables.

4.1.1. Primary outcome:

- Children's long-term survival without neurodevelopmental disability

4.1.2. Secondary outcomes:

- Offspring
 - Time to birth
 - Preterm birth before 37 weeks: rate of delivery before 36+6 weeks
 - Preterm birth before 34 weeks: rate of delivery before 33+6 weeks

Confidential

[figure not shown]
[figure not shown]
- Preterm birth before 32 weeks: rate of delivery before 31+6 weeks

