Women with a singleton pregnancy at 12+0 – 16+0 weeks of gestation and a history of at least one previous preterm delivery before 34+0 weeks and/or a history of previous cervical surgery attending the reference hospital for a preventive examination will be informed of the ongoing trial. The patient will be advised of the intended therapeutic effect and possible side effects. If they agree and after obtaining their informed consent, they will be randomised according to either usual management (=control group) or cervical pessary placement up to 37+0 weeks (=pessary group).

If the pregnant woman is assigned to the pessary group and after having excluded a vaginal infection the pessary will be inserted directly. This procedure does not need anaesthesia and it does not need to be done in a surgery room. After the insertion of the pessary the correct fit of the pessary is verified by transvaginal ultrasound and in case it does not fit perfectly, it can easily be adjusted.

In the control-group the cervical length of the women will be evaluated by transvaginal ultrasound scan started from randomization and every 4 weeks; if a cervical shortening below 25mm is detected a Mc Donald cerclage will be placed.

The pessary will be removed at 37+0 weeks of gestation, or before if any unexpected event occurs (see 4.6). After insertion of the pessary the obstetrical management during the remainder of the pregnancy will be usual management.

Further surveillance of the pregnancy will not be influenced by the participation on the study.

4.5. Expected duration of subject's participation.

Starting recruitment: June, 1st, 2018

Finishing recruitment and follow-up: est. June 1st, 2023.

Final report: Sept. 1st, 2023

4.6. Completion and interruption criteria of the study or the subjects.

The pessary will be removed at 37+0 weeks of pregnancy. The indications to remove them before this time will be: active bleeding stronger than period bleeding, persistent contractions after tocolysis and premature rupture of the membranes after 34+0 weeks.

After removing the pessary, the obstetrical management will be done as usual and will not be influenced by the study.

4.7. Maintenance of the randomisation codes and test procedures of the trial.

Every participating centre will have its own randomisation list.

We have created a database in a website so it can be accessed worldwide, that every hospital will be able to randomize their patients.

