Every center will receive a password and a username in order to access the database for recruitment, randomization and documentation of patient data. Hereby, a personal identification number will be assigned for every patient. Patient names will not appear in the databases.

This database will be supervised and coordinated by PD [name], Bürgerhospital Frankfurt/M. (Webmaster).

4.8. Identification of data to be collected in the case report files (CRF) that should be considered as data source.

Data will be collected in E-CRF, provided by >[name] Wissenschaft, Berlin< on study software "Castor".

4.9. Definition of what is considered to be the end of the study.

The study will be finished after the 3 year-follow up examination of the surviving children focusing on neurodevelopmental disabilities.

5. Selection and withdrawal of subjects

5.1. Inclusion criteria.

- Women with a singleton pregnancy and a history of at least one previous preterm delivery before 34+0 weeks and/or a history of previous cervical surgery
- 12+0 -16+0 weeks of gestation
- Minimal age of 18 years
- Informed consent signature

5.2. Exclusion criteria.

- Major fetal abnormalities (requiring surgery or leading to infant death or severe handicap)
- Cerclage prior to randomisation
- Uterine malformation
- Placenta previa totalis
- Active vaginal bleeding at the moment of randomization
- Spontaneous rupture of membranes at the time of randomization
- Silicone allergy
- Painful regular uterine contractions
- Current participation in another RCT

5.3. Withdrawal criteria.

If a participant may voluntarily withdraw from treatment or if it is necessary to remove the pessary due to the conditions described before, the patients will be followed as usual until delivery (intention-to-treat analysis).

Replacement of patients is not applicable in this trial.

5.4. Rescue treatment criteria.

Regarding the control group, a McDonald cerclage may be indicated if there is a cervical shortening below 25 mm during the follow-up scans according to the current guidelines and expert recommendations¹¹.

6. Treatment of Subjects

6.1. Treatments to be administered.

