The pessary will be inserted during a preventive examination in pregnancy in the examination room. This procedure does not need anaesthesia and it does not need to be done in a surgery room. After the insertion of the pessary the correct fit of the pessary is verified by transvaginal ultrasound and in case it does not fit perfectly, it can easily be adjusted. In the control-group the cervical length of the women will be evaluated by transvaginal ultrasound scan: if a cervical shortening below 25 mm is

Confidential

detected a cervical cerclage will be placed. The pessary or cerclage will be removed at 37+0 weeks of gestation, or before if any unexpected event occurs (see 4.6). After insertion of the pessary the obstetrical management during the pregnancy will be usual management. Further surveillance of the pregnancy will not be influenced by the participation on the study.

7. Efficacy assessment

7.1. Specification of efficacy parameters: Primary and secondary endpoints.

This study aims to investigate the benefit of a prophylactic cervical pessary treatment in women at high risk of PTB due to a history of at least one previous preterm delivery before 34+0 weeks and/or a history of previous cervical surgery on the perinatal outcome and on the children's long-term survival without neurodevelopmental disability.

The effect of the pessary treatment will be assessed in women independent of the cervical length at 12 -16 weeks of gestation compared to standard care treatment.

7.2. Methods and timing to assess records and analyze the efficacy parameters.

The pregnant women will be assessed according to usual obstetrical management in a high-risk pregnancy.

	Regular Preventive Exam	Serial CL measurements after randomization	Regular Preventive Exam 37 WoG	Postnatal evaluation	3 years follow up (corrected age)
Study procedure	study inclusion 12+0-16+0 WoG				
Informed consent	x				
randomisation	x				
Control-group		x			
Pessary/cerclage placement	Pessary-Group: Pessary at enrollment	Control-Group: Cerclage when CL \leq 25mm			
Pessary/cerclage removal	WoG 37+0		x		
physical exams					
Abdominal US	x	x	x		
Vaginal US		x			
pH-Value	pH < 4,4	pH < 4,4			
Neonatal examination				x	
Ages & Stages test					x
Exam at paediatrician					x

8. Assessment of Safety

8.1. Procedures to record and report adverse events.

Confidential

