(2) The primary outcome will be evaluated 3 years after the last woman enrolled in this study has delivered her neonate.

Confidential

A descriptive analysis by preterm birth will be carried out calculating means and medians for quantitative variables and proportions with 95% confidence intervals for categorical variables.

Additionally we will perform an explorative subgroup analysis of the study collective comparing the efficacy of the cervical pessary treatment in women with a normal cervical length at 12 -16 weeks of gestation and in women who have developed a cervical shortening (< 25 mm) as an additional risk factor.

For the primary endpoint we expect to have a drop out rate of up to 25% due to the long follow-up time (3 years) of the study; but we do not expect to have lost data for the secondary endpoints because for these parameters the study has a short follow-up time till time to birth only.

An interim analysis shall be conducted on key safety parameters after birth of 150 neonates: the following safety endpoints will be assessed by a one-sided test with $\alpha=1\%$

- on level of the neonates:

rate of preterm birth, time to birth, birth weight, death, neonatal morbidity, harm of intervention

- and on the maternal level:

rate of hospitalisation for threatened preterm labour < 32 weeks, rate of P_{RoM} <32 weeks, rate of infection / inflammation, rate of physical or psychological intolerance to pessary, rate of SAR/SAE, death.

The trial will be terminated as negative if a disadvantage for the pessary-treatment can be found in one of these tests. To guarantee a high safety level the significance level is chosen more conservatively than in a Bonferroni correction. All analysis will be carried out with SPSS® version 19.0 or later (IBM Company SPSS Inc.

Headquarters, Chicago, Illinois, USA) and R version 3.2.3 or later (R Foundation for Statistical Computing, Vienna, Austria).

Primary Outcome	Statistical Test
Children`s Long-Term Survival without Neurodevelopmental Disability (3-Years-follow up)	Chi-Square test
Secondary Outcome	Statistical Test
Birth before 34 Weeks of Gestation	Chi-Square test or Fisher test
Time to Birth	Cox regression
Birthweight	t-test or Wilcoxon-Mann-Whitney test
Fetal / Neonatal Death	Chi-Square test or Fisher test
Neonatal Morbidity	Chi-Square test or Fisher test
Need for Hospitalization	Chi-Square test or Fisher test
Days of Hospitalization	t-test or Wilcoxon-Mann-Whitney test

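### The shortened-cervix stratum of the exploratory subgroup analysis is undated; on its most natural reading it forms after randomisation, so its between-arm contrast is not a randomised comparison

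*Combined protocol and SAP*

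**What the plan says.** Section 9.1 announces an "explorative subgroup analysis of the study collective" that compares pessary efficacy in two strata. The first is tied to the enrolment window: normal cervical length at 12-16 weeks. The second is efficacy "in women who have developed a cervical shortening (< 25 mm) as an additional risk factor", with no gestational age, visit or scan named. It is the only subgroup analysis in the plan.

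On scanning, the protocol says the following:

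- Synopsis, study design: "serial cervical length measurements should be conducted onward the 12+0 week every 4 weeks". No arm is named, but the sentence follows from the control-arm cerclage rule.
- Synopsis, study population: "patients of the control arm shall receive serial cervical length measurements by transvaginal ultrasound (TVS) every 4 weeks started at 12+0 weeks".
- Section 2.2: "In the control group serial cervical length measurements shall be conducted every 4 weeks in order to diagnose cervical shortening as soon as possible".
- Section 4.4, in a sentence about the control group: "the cervical length of the women will be evaluated by transvaginal ultrasound scan started from randomization and every 4 weeks".
- Sections 4.4 and 6.1, pessary arm: a transvaginal scan after insertion to check the fit. No serial length scans are described.

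On what follows a short cervix in a control woman, section 5.4 says that cerclage may be indicated "if there is a cervical shortening below 25 mm during the follow-up scans", and the synopsis also uses permissive wording in one place. Section 6.1 says that once shortening is "detected a cervical cerclage will be placed", and section 4.4 is equally firm.

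**The concern.** A subgroup keeps the protection of randomisation when membership is fixed before allocation. The pessary is placed at enrolment, so any shortening found later occurs under the assigned treatment. If the pessary changes who shortens, the pessary women and control women in the shortened stratum are different kinds of women, and their outcomes can differ without any effect of the device on outcome.

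Two features add to this. If one arm is scanned for length every four weeks and the other is not, the stratum also depends on who was looked at. And a woman who is normal at 12-16 weeks and shortens later belongs to both strata, so the two results are not a clean contrast.

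The stake is interpretation. The rationale presents the pessary as a good option once shortening develops, so a shortened-cervix result is likely to be read as showing in whom the device works or harms.

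**Working it through.** The plan states no figure for this analysis, so there is none to reproduce. The check is a reading of the text, followed by an illustration.

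**1. Is the second stratum formed before or after randomisation?**

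- For after: section 9.1 dates the first stratum and not the second, and its verb describes something that has come about. Section 5.4 treats shortening below 25 mm as a finding of follow-up scans. The schedule table in section 7.2 places serial length measurement after randomisation. The rationale uses the same verb for shortening that arises during pregnancy.
- For before: section 7.1 says efficacy is assessed whatever the length at 12-16 weeks, a short cervix is not an exclusion criterion, and the first stratum presupposes a length at 12-16 weeks.

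The balance favours after. The text does not settle it.

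**2. Is shortening looked for equally in both arms?** Three places describe four-weekly scans for controls (synopsis, 2.2, 4.4). One sentence names no arm. No text schedules them for the pessary arm and none excludes them. Detection may therefore differ; the documents do not show that it does.

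**3. What does conditioning on later shortening do?** Every input here is an assumption except the 155 women per arm (section 9.2). Let a share s_c = 33% of controls shorten and a share s_p shorten under the pessary. Women who shorten in either arm have event risk r_H; women who shorten only without a pessary have r_M. The pessary has no effect on any woman's outcome, and detection is complete in both arms.

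Control risk in the stratum = [s_p × r_H + (s_c − s_p) × r_M] / s_c. Pessary risk in the stratum = r_H. The relative risk (RR) is their ratio; the risk of women who never shorten does not enter.

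If the prevented cases are the lower-risk ones (r_H = 35%, r_M = 25%):

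- s_p = 33%: RR = 1.00
- s_p = 25%: control risk (0.25 × 0.35 + 0.08 × 0.25) / 0.33 = 32.6%; RR = 1.07
- s_p = 16.5%: control risk (0.165 × 0.35 + 0.165 × 0.25) / 0.33 = 30.0%; RR = 1.17
- s_p = 10%: control risk (0.10 × 0.35 + 0.23 × 0.25) / 0.33 = 28.0%; RR = 1.25

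If the prevented cases are the higher-risk ones (r_H = 25%, r_M = 35%):

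- s_p = 25%: control risk 27.4%; RR = 0.91
- s_p = 16.5%: control risk 30.0%; RR = 0.83
- s_p = 10%: control risk 32.0%; RR = 0.78

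The true RR is 1.00 throughout. Unequal detection alone gives the same middle values: if half of pessary-arm shortening is detected and the detected half has risk 35%, 30% or 25% against 30% in controls, RR = 1.17, 1.00 or 0.83.

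**4. Precision.** At s_p = 16.5% the stratum holds about 155 × 0.33 = 51.2 control women and 155 × 0.165 = 25.6 pessary women. Expected events are 15.3 and 9.0. SE(log RR) = sqrt(1/8.95 − 1/25.6 + 1/15.3 − 1/51.2) = 0.344, so the 95% interval around 1.17 is 0.59 to 2.29. Random error would exceed the bias in this example.

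**The case against.** The best defence is that the stratum may be a baseline one. The rationale treats a short cervix as a risk factor that can be combined with previous preterm birth and says the two should be addressed separately; section 9.1 echoes that by calling shortening an additional risk factor. If it means short at entry, measured before allocation in both arms, the subgroup is valid. That reading is possible, which is why the conclusion is conditional. But the text would still have to say so and to secure the measurement.

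It is also fair that the analysis is exploratory, that no decision rule uses it, and that the primary comparison is untouched. This limits the severity. It does not remove the point, because an exploratory label does not tell a reader that the groups being compared are not randomised ones.

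Three stronger readings might be inferred, and the documents do not support them:

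- *That comparison with cerclage is itself a bias.* Controls found short may or will receive cerclage, so this stratum compares pessary largely with cerclage. That is the trial's control strategy, and it applies to the primary comparison too. It bears on interpretation, and a baseline definition does not change it, because controls short at entry can also meet the cerclage rule.
- *That no entry length is taken.* The schedule table marks no vaginal ultrasound at inclusion, but it marks none there for the fit scan either, although the pessary is placed at enrolment. The missing mark is weak evidence, and the section 4.3 flowchart is not visible in the text reviewed.
- *That pessary women are not scanned for length.* The documents are silent on this.

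**Conclusion.** The point holds in conditional form. The second stratum is undated. If it means shortening after randomisation, as the wording most naturally suggests, its between-arm contrast is not protected by randomisation, whether or not both arms are scanned equally. Possible differences in detection and the overlap of the strata add to this.

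The direction of the bias is not determined and its size cannot be derived from the documents. The range of 0.78 to 1.25 rests wholly on assumed shares and risks and shows only that either direction is possible. A reader might infer something larger, such as a spurious halving of risk or a 50% increase. That needs an extreme allocation: for example, shortening risks of 20% and 60%, with all prevention or all detection falling in one of those two groups. Nothing in the documents supports such inputs.

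The change is worth making before outcome data are analysed, because an undated definition leaves room to choose it after the results are seen. Confidence is medium, because the baseline reading cannot be excluded.

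**What to change.** In section 9.1:

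- Define the cervical-length subgroup by a length recorded before allocation in both arms, with two non-overlapping categories (25 mm or above; below 25 mm). Report a treatment-by-subgroup interaction estimate with its confidence interval, labelled exploratory.
- Report later shortening only descriptively by arm, stating how and how often it was ascertained in each. Label any between-arm contrast within it as non-randomised.
- If no pre-allocation length is recorded in both arms, omit the efficacy subgroup.

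Reconcile the start of scanning between the synopsis (12+0 weeks) and section 4.4 (from randomisation), and state when the entry length is taken. The permissive and firm wordings on cerclage also need to be reconciled, so that the comparator in this stratum can be described.

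Cost: a wording change if an entry length is already recorded in both arms. If not, adding it is a small procedural change, and it cannot be recovered for women already randomised. The short-at-entry stratum may be small: if 2% to 10% are short at entry (an assumption), 310 × 0.02 = 6 to 310 × 0.10 = 31 women over both arms, so the interaction estimate will be imprecise. An efficacy claim for women who shorten later is given up.
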